Consent, Enrollment, and Treatment Assignment. To facilitate enrollment, the trial will be discussed with the parents of potentially eligible infants as soon as feasible after the parent(s) have been informed by the medical staff that their infant has NEC or IP, whether or not there has been a decision to perform surgery. (Depending on the center and circumstances, this discussion might include the coordinator, attending neonatologist, fellow, and/or pediatric surgeon). In addition to printed informational materials, the development of a brief explanatory video or DVD is being considered which would explain the rationale for the trial and provide a standardized method of starting the informed consent process. Informed consent will be diligently sought for both randomization and collection of pre-discharge and follow-up data. If refused, consent will then be sought only for data collection. We propose to allow variability in the consent process at individual centers with the overall goal in common of achieving as high a consent rate as possible. One method we are proposing is to have provisional consent for the trial obtained by the neonatologist or Network research coordinator initially. If the family has given this provisional consent, the attending pediatric surgeon would then assess the infant for inclusion in the study. If the surgeon agrees to randomize the infant then enrollment would occur. If the family has not agreed to the initial / provisional consent, the surgeon could also discuss the trial with the family and consent might be obtained at that time. Infants will be enrolled by calling the RTI International (RTI). During "standard hours" this would ideally be done by the Network coordinator. To avoid baseline differences, randomized infants will be stratified according to two variables: center; and according to the overall risk for death or NDI (higher / lower) at enrollment. The risk stratification formula was primarily developed in the prospective observational model and includes the following variables: birth-weight, gestational age, vasopressor requirement (yes / no), if infant is on high frequency (oscillating or jet) ventilation

or not (any modality of conventional ventilation or no mechanical ventilation), pH, FiO₂, and preoperative diagnosis (NEC or IP). (There is no intent to power the trial to compare all subgroups). A variable, permuted, block size will be used.

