Stratification according to preoperative diagnosis. A unique design feature of this trial (as compared to the two prior RCTs in this patient population) is the stratification utilizing the presumed preoperative diagnosis (NEC or IP). We feel it is critical to make this distinction, to the best of our ability, to ensure maximal comparability of treatment groups and to have the ability to test for interactions between treatment and diagnosis. Based on the Network observational study and other data, the following patient characteristics support a preoperative diagnosis of NEC: presence of pneumatosis on KUB, older age at operation (mean age at operation from observational study = 27.8 days), and presence of portal vein air. A history of enteral feedings prior to disease occurrence has been suggested as supportive of a diagnosis of NEC in other publications. In the Network observational study, only 46% of patients with proven NEC (determined at laparotomy) had a pneumoperitoneum on preoperative imaging.³

The following characteristics support the diagnosis of IP: younger age at operation (mean age at operation in Network observational study = 7.4 days), absence of pneumatosis, and presence of pneumoperitoneum on preoperative KUB. Other characteristics that have been used to favor a diagnosis of IP include the radiographic finding of “gasless abdomen” and the physical exam finding of a “blue abdomen”. In the Network observational study, the last two characteristics were not statistically different between NEC and IP infants, but the findings supported using these as secondary determinants to help distinguish the two diagnoses.

In the Network observational study, the correlation of the preoperative diagnosis (NEC or IP) with intraoperative diagnosis in patients undergoing laparotomy was 95%. While recognizing that the distinction is not perfect preoperatively, we feel that this is a positive design feature and preoperative diagnosis of the pediatric surgeon will be recorded. Accuracy of this distinction will again be measured in those undergoing laparotomy.

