4. patient is at a center able to perform both laparotomy and drainage.

Exclusion Criteria:

1. Major anomaly which influences likelihood of developing primary outcome or affects surgical treatment considerations;
2. congenital infection;
3. Prior laparotomy or peritoneal drain placement,

4. Prior NEC or IP,
5. Follow-up unlikely (e.g., mother incarcerated, or currently resides (or plans to move) far from any Network center.), and
6. Infant for whom full support is not provided (including surgical treatment).

Method of Treatment Assignment and Randomization

Infants enrolled into the randomized cohort will be randomized using a variable, permuted, block size scheme. Infants will be randomized by calling RTI International as soon as a decision to perform surgery is made (or via a computer randomization process). Randomized infants will be stratified according to two variables: center and according to the overall risk for death or NDI (higher / lower). The risk stratification formula was primarily developed in the prospective observational model and includes the following variables: birth-weight, gestational age, vasopressor requirement (yes / no), if infant is on high frequency (oscillating or jet) ventilation or not (any modality of conventional ventilation or no mechanical ventilation), pH, FiO₂, and preoperative diagnosis (NEC or IP). Treatment beyond the initial surgical management will be unaffected by the trial.

Treatment Masking

As this is a surgical trial, the surgeons will not be masked to randomized treatment. Outcome assessments at 18-22 months will be assessed by evaluators who are masked to the details of the operative intervention(s) that have been performed using standard Network assessments. The statistician is unmasked in this trial.

Sequence of Planned Analyses

Interim Analyses

Annual Data Safety Monitoring Committee (DSMC) meetings will be convened to monitor the progress of the trial and review the accruing safety and efficacy data. Starting one year after at least 11 sites have IRB clearance to start enrolling into the trial, safety data will be monitored. Once follow up data start becoming available (which should occur from the 2nd year onwards) interim efficacy data will also be presented to the DSMC. All figures, summaries, and listings created in the interim analyses and presented to the DSMC will be masked to treatment assignment, but interim analysis results will be unmasked at the DSMC's request.

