The primary analysis of randomized cohort data will assess the effect of treatment on death or NDI at 18-22 months corrected age, death, and other clinical outcomes as defined in Study Endpoint section above (pages 8-10) and listed on pages 13 and 14. This analysis will be performed using a robust Poisson regression model identical to the model defined on page 17 and 18. If possible center will also be included in the model as a fixed or random effect. The default will be a fixed effect, but a random effect may be used if model convergence issues results from using a fixed effect. The outcome variable will assign one to the event of death or NDI at 18-22 months corrected age and zero otherwise. The treatment variable will assign one to laparotomy and zero to drainage. It follows that relative risks less than one (or less than zero on the log scale) will favor Laparotomy.

Like the efficacy interim analysis, the final test statistic produced for the treatment effect will be a z-statistic. This z-statistic will be compared to the appropriate boundary pair calculated from the updating call to `gsDesign()` as described in the efficacy interim analysis section. As with the interim efficacy analyses, the actual robust regression modeling at each interim analysis will be completed in SAS, and a figure summarizing the final analysis results will be constructed in Excel. This figure will contain information from all prior interim efficacy analysis results.

In addition to the above formal adjusted analyses, simple unadjusted treatment comparisons of randomized data will be completed, and 95% confidence intervals of differences in proportions will be constructed. The formatting of these tabulations will be determined as the corresponding papers develop.

Secondary Analysis of Primary Outcome Using Randomized Cohort Data

The analyses will include an assessment of whether there is an interaction between treatment (laparotomy or drainage) and disease (NEC or IP). This assessment will use a robust Poisson regression model with will include treatment (laparotomy or drainage), preoperative diagnosis (NEC or IP), and the treatment by preoperative diagnosis interaction. If the Wald test for the interaction term has a p-value less than 0.05, then the conclusion will be the study has produced evidence of an interaction between treatment and pre-operative diagnosis with respect to the primary outcome. If such

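### The protocol presents randomization as stratified by NEC or IP, but diagnosis enters only through a two-level risk score, and the SAP's interaction model does not name that risk stratum

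*Protocol*

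**What the plan says.** The protocol has a section headed Stratification according to preoperative diagnosis. It says that a feature distinguishing this trial from the two earlier randomized trials "is the stratification utilizing the presumed preoperative diagnosis (NEC or IP", and that drawing this distinction is critical "to ensure maximal comparability of treatment groups and to have the ability to test for interactions between treatment and diagnosis". It adds that the surgeon's preoperative diagnosis will be recorded.

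The scheme itself is in the section just before, Consent, Enrollment, and Treatment Assignment: "randomized infants will be stratified according to two variables: center; and according to the overall risk for death or NDI (higher / lower) at enrollment". The abstract gives the same two factors, and so does the SAP under Method of Treatment Assignment and Randomization: "Randomized infants will be stratified according to two variables: center and according to the overall risk for death or NDI (higher / lower". The risk formula has seven inputs: birth weight, gestational age, vasopressor use, high-frequency ventilation, pH, FiO₂ and preoperative diagnosis. Neither document gives its weights or the cut-point between higher and lower.

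For the interaction, the SAP (Secondary Analysis of Primary Outcome Using Randomized Cohort Data) specifies a "robust Poisson regression model with will include treatment (laparotomy or drainage), preoperative diagnosis (NEC or IP), and the treatment by preoperative diagnosis interaction". It writes no formula and mentions neither risk level nor center. The decision rule begins "If the Wald test for the interaction term has a p-value less than 0.05"; if it is met, NEC and IP effects are estimated separately. The SAP's primary model, by contrast, contains treatment, risk level and, if possible, center.

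**The concern.** Whether the better operation depends on diagnosis is the protocol's second objective and its fourth secondary aim. A reader of the protocol section would take NEC and IP to be separate randomization strata, with the arms balanced within each. The randomization does not do this. At one center, NEC and IP infants with the same risk level are drawn from the same block sequence, so the arms can differ by chance in their NEC share and in their risk mix within NEC or IP.

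The risk stratum is the adjustment the trial already has for that second kind of imbalance, and the interaction model does not list it. At stake are an accurate description of the design and some precision for a named secondary question.

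**Working it through.** **1. The texts side by side.** The protocol's diagnosis section implies three factors (center, risk, diagnosis). The operative text names two, three times: protocol abstract, protocol enrollment section, SAP. For the models, the SAP's primary and interim efficacy models include risk, and its other interaction model (treatment by baseline risk, under Interim Mortality Assessment) is written out with risk and center. The treatment-by-diagnosis model lists neither.

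**2. Sample size, for reference.** For 80% v 65%, two-sided Fisher exact test at 0.05, exact power is 0.803 at 150 per arm and 0.799 at 149. The stated 300 reproduces, and nothing below changes it.

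**3. Chance imbalance in diagnosis.** From the protocol: N = 300, equal allocation, 16 centers, hence 16 × 2 = 32 strata of about 300/32 = 9.4 infants. Assumed: NEC share p of 30% or 50%, blocks of 2, 4 or 6, equal centers, and a gap g = P(high risk | NEC) − P(high risk | IP), with P(high risk | NEC) = 0.5 + g/2.

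Approximately, SD of the between-arm difference in NEC share = √(4V/N), where V is the average variance of the NEC indicator within risk level.

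- g = 0, p = 0.5: V = 0.25, SD = √(1.00/300) = 5.8 points
- g = 0, p = 0.3: V = 0.21, SD = √(0.84/300) = 5.3 points
- g = 0.6, p = 0.5: NEC share is 0.8 in high and 0.2 in low risk, V = 0.16, SD = √(0.64/300) = 4.6 points

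Simulation of the actual blocking agrees:

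| NEC share | g | SD, current scheme (points) | Difference above 10 points | SD if diagnosis were a stratum (points) |
|---|---|---|---|---|
| 30% | 0 | 5.3 | 5.5% | 2.8 |
| 30% | 0.3 | 4.9 | 3.9% | 2.8 |
| 30% | 0.6 | 4.5 | 2.4% | 2.6 |
| 30% | 0.9 | 3.0 | 0.0% | 2.3 |
| 50% | 0 | 5.9 | 9.1% | 2.7 |
| 50% | 0.3 | 5.4 | 6.6% | 2.6 |
| 50% | 0.6 | 4.8 | 3.9% | 2.6 |
| 50% | 0.9 | 3.0 | 0.1% | 2.1 |

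The last column is for scale only. For g from 0 to 0.6 the SD is 4.5-5.9 points. At g = 0.9, where risk nearly coincides with diagnosis, most of the problem disappears.

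**4. The interaction model.** 1,500 simulated trials per row, N = 300, 16 centers. Assumed: high v low risk ratio 1.3, center SD 0.1 on the log scale, robust Poisson regression. Entries are the percentage with interaction p < 0.05.

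| True RR in NEC / IP | NEC share, g | SAP's three terms | + risk | + risk + fixed center |
|---|---|---|---|---|
| 0.8125 / 0.8125 | 50%, 0.3 | 4.6 | 5.0 | 6.1 |
| 0.8125 / 0.8125 | 30%, 0.3 | 5.1 | 5.1 | 6.7 |
| 0.70 / 0.95 | 50%, 0.3 | 54.4 | 56.4 | 57.3 |
| 0.70 / 0.95 | 30%, 0.3 | 44.7 | 47.0 | 48.0 |
| 0.70 / 0.95 | 50%, 0.6 | 55.1 | 56.0 | 56.3 |

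The simulation error of a 5% rate is √(0.05 × 0.95/1500) = 0.56 points. The three-term model therefore holds its level, while 6.1-6.7% with fixed centers lies about 2-3 standard errors above 5%. In the first row the empirical SDs of the interaction are 0.147, 0.144 and 0.148. Adding risk gives a variance ratio of (0.147/0.144)² = 1.04; adding fixed centers as well gives (0.147/0.148)² = 0.99, so the gain is lost.

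**5. Dependence on the assumed risk effect.** With no true center effect and a range of assumed stratum risks, the variance ratio for adding risk alone was 0.99-1.17, at most a cut of 1 − 1/1.17 = 15%. Adding fixed centers as well gave 0.93-1.11. The low end fits the only stratum effect in the documents, the illustrative simulation in SAP Statistical Appendix B (80% v 0.94 × 80% = 75.2%), which is not a planning estimate. Contrasts as wide as 98% v 59% in the drain arm sit at or slightly above the high end.

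**The case against.** The protocol says that the stratification utilizes diagnosis, and the section immediately before explains how: through the risk formula. Diagnosis is therefore not absent from randomization. Since the weights and cut-point are not given, the strata might separate NEC from IP quite well. Randomization also leaves diagnosis balanced in expectation. On the model, the SAP says what will be included and excludes nothing, and the protocol's Statistical Analyses section puts the stratifying variables in the regression before it mentions the interaction. The SAP states that only the primary hypothesis was powered, and a footnote says the interaction will be read clinically rather than as statistical significance.

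Most of this stands, and it rules out several stronger readings. A reader might infer that diagnosis plays no part in the allocation; it does, with unknown weight. A reader might infer that the interaction cannot be tested without stratifying on diagnosis; it needs only a baseline record, which the protocol provides. A reader might infer that the three-term model is biased or has the wrong error rate; the simulations show neither. A reader might expect a large gain in precision; that depends on risk contrasts the documents do not supply.

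The mismatch remains. The heading and stated purpose of the protocol section go beyond what a two-level score can assure. Despite its footnote, the SAP attaches a p < 0.05 rule that decides whether separate NEC and IP effects are produced, so the covariates behind that p-value should be explicit.

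**Conclusion.** The protocol overstates what its randomization does: stratification does not assure balance by diagnosis. Unless the risk level closely tracks diagnosis, a chance difference in NEC share with an SD of about 4.5-6 points is to be expected, exceeding 10 points in about 2-9% of trials. The SAP's interaction model does not name a stratum that the trial randomizes by and the primary model carries. Adding it is worth about 0-15% of the interaction variance and, in the scenarios run, about 1-3 points of power. These figures rest on assumed NEC shares, risk-diagnosis association, block sizes, and risk and center effects. This is a correction of wording plus a nearly free improvement to a secondary analysis, not a threat to validity.

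**What to change.** 1. Protocol, section on preoperative diagnosis: say that diagnosis enters randomization only as an input to the risk level, and that stratification does not assure balance by diagnosis. Keep the interaction as an aim that rests on the recorded diagnosis.
2. SAP, treatment-by-diagnosis model: add the risk stratum, write the formula out, and take the NEC and IP effects from that model.
3. Tabulate risk stratum by arm within NEC and within IP.
4. Make center adjustment in this model optional or a random effect, and say so in advance. Fixed center effects can cost precision and slightly raise the type I error. The SAP's random-effect fallback applies only to convergence trouble, so it would not prevent this.

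The cost is wording, one covariate already in the dataset and one table. Randomization, sample size and the primary analysis do not change. Because the SAP leaves the statistician unmasked, the model should be fixed before the interaction result is examined.

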Data regarding the value of subsequent laparotomy are minimal. In a Pubmed search using “salvage laparotomy and necrotizing enterocolitis” only 6 articles were identified. (2/12/09) In one study specifically addressing this issue, 17 patients were treated with drainage over a 5 year period and only 4 of these had a subsequent laparotomy.²⁶ These 4 did have a 100% mortality rate vs. 46% mortality in the 13 patients treated with drain only, but these are very small patient numbers from which to make treatment recommendations. Goyal et al., reviewed an 18 year experience and had 42 patients treated with initial drainage. Eleven patients had what was considered to be a poor response to drainage, 6 of these had a rescue laparotomy and 3 survived. These authors considered rescue laparotomy after drainage to be beneficial.²⁷ Sharma et al. reported 32 infants treated with initial drainage, 8 of whom had an early subsequent laparotomy with 5 survivors and these authors also considered early subsequent laparotomy to be an important and useful therapy.²⁸

In the prospective observational study done by the NICHD Neonatal Research Network, 80 infants had an initial drain placement. Only 18 of these (22.5%) had a subsequent laparotomy. In the group treated with drainage only (n=62), the mortality rate was 55%. The mortality rate in the group initially treated with drainage, followed by a subsequent laparotomy, was 68%. The low percentage of patients treated with a subsequent laparotomy after initial drainage provides some evidence that drains are often used as planned definitive therapy, rather than a temporizing measure.^{2,3} The high mortality rate in the group of patients that did have a subsequent laparotomy (68%) should give caution to surgeons choosing to employ this treatment strategy.

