The UK randomized trial (Rees et al) allowed infants randomized to initial drainage to undergo a subsequent laparotomy \geq 12 hours later if the infant's condition had deteriorated (at the discretion of the surgeon).⁵ Infants who were improved or were considered stable did not have a subsequent laparotomy. In this trial, 35 infants were randomized to initial drain placement and 26 did undergo subsequent laparotomy (74%). The median time of the subsequent laparotomy was 2.5 days (range: 0.4 – 21 days). Indications for the laparotomy were clinical deterioration (14), increasing / persistent pneumoperitoneum (12), palpable mass and continued pneumoperitoneum (1), stool drainage from drain site (1), intestinal obstruction (2) (some had more than one of these indications). The relative risk for mortality in the Drain + Laparotomy subgroup was 1.4 (95% CI: 0.6-3.4; p=0.4) compared to the initial laparotomy group. The survival curves show the drain + laparotomy group to be intermediate between the initial laparotomy group and the drain group, with no significant differences between any of the 3 subgroups analyzed. The drain only group in this trial had a mortality rate of 49% compared with 36% for laparotomy. Drain + subsequent laparotomy had an intermediate mortality rate of approximately 42% (exact data not published).

The Moss trial protocol discouraged subsequent laparotomy after initial drainage, stating that infants that survive after initial drainage often deteriorate early but then improve.⁴ The protocol does allow early subsequent laparotomy for persistent metabolic acidosis, hemodynamic instability, and respiratory failure, and later laparotomy for obstruction. This trial randomized 55 infants to drainage, 5 of whom had subsequent laparotomy for clinical deterioration (9%) between days 2 and 45 after the initial procedure. Four of these 5 survived. Sixteen additional patients had delayed laparotomy.

Conclusions regarding subsequent laparotomy after initial drainage:

1. When US surgeons are allowed to decide initial treatment (i.e. observational study), the use of subsequent laparotomy is uncommon (approximately 20%).
2. If the initial treatment is chosen by randomization, rather than surgeon preference, the subsequent laparotomy rate may be higher. This is due to the fact that some infants would be randomized to drainage that the surgeon would have treated with laparotomy if chosen by preference.

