Follow-up Evaluation. Infants will be assessed at 18 to 22 months of age, corrected for prematurity, according to the NICHD Neonatal Research Network Follow-up Study Protocol (rev. 10.31.2007) and Manual (rev. 2.28.2008). The follow-up visit includes the following assessments or structured inquiries: medical history including neurosensory outcomes, physical and neurological examination, neurodevelopmental evaluation with the Bayley Scales of Infants Development III, social/behavioral evaluation with the Brief Infant Toddler Social Emotional Assessment (BITSEA), and demographics and socioeconomic status questionnaires. Examiners are certified according to the procedures described and approved by the NICHD Neonatal Research Network.

Neurodevelopmental impairment (NDI) is defined as meeting any of the following criteria: moderate to severe cerebral palsy (CP) with Gross Motor Function Classification System (GMFCS) Level ≥ 2 , a Bayley III Cognitive score < 85 , < 20 -200 bilateral vision, and/or permanent hearing loss that does not permit the child to understand the directions of the examiner and communicate despite amplification.

The components of NDI are defined as follows:

Cerebral Palsy: Definite abnormalities in classical neuromotor exam, including tone, deep tendon reflexes, coordination and movement, coupled with a delay in motor milestones with a disorder of motor function. Severity of CP is classified according to the GMFCS level.³⁰ Moderate CP is defined as GMFCS level 2 or 3; severe CP is defined as GMFCS level 4 or 5.

Psychometric testing: Cognitive outcome at 18-22 months will be assessed by certified psychologists or psychometricians using the BSID III. For this study, the cognitive subtest (mean \pm SD: 100 \pm 15) will be administered. Scores on the cognitive subtest of <70 (>2 SD below the mean) is consistent with severe cognitive impairment.

Sensory deficits are identified through specific question concerning vision and hearing. Children with no useful vision in either eye is consistent with a refraction definition of <20/200 (legally blind). Permanent hearing impairment that does not permit the child to understand the directions of the examiner and communicate despite amplification is consistent with severe auditory impairment and would be adequate to meet the definition of NDI.

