An important issue (for this trial and for neurodevelopmental assessment of premature infants in general) is the potential difference in sensitivities of the Bayley II and III products in defining NDI. Some authors have reported recently that the Bayley III likely underestimates NDI, compared to the Bayley II.³¹ Because of these issues, for this trial a Bayley III score of <85 will be one of the conditions defining NDI (in addition to those above).

Blinding and Reliability. Blinded collection of predischarge data would not be reasonably feasible for our research nurses. Follow-up personnel who are not told the treatment group will assess all follow-up findings. Because patients in each treatment group are likely to require laparotomy after the initial surgical procedure, it will be difficult to predict treatment group assignment at 18-22 months by simply examining the child, as infants in both groups may have undergone multiple abdominal procedures. The final assessment of impairment will be reviewed by three subcommittee members without knowledge of treatment group who will adjudicate the outcome of any infants whose outcome is uncertain (as was done Hypothermia trial).

Statistical Analyses. The primary analysis will assess the effect of treatment on death or NDI at 18-22 months corrected age. This analysis will be performed using standard statistical analyses often used in multicenter trials: logistic regression equations in which the predictor variables include treatment group and the stratifying variables (in this trial, center, and risk stratification formula). The analyses will include an assessment of whether there is an interaction between treatment (laparotomy or drainage) and disease (NEC or IP). Bayesian analyses^{11, 15} of the primary outcome will also be performed because statistical power will be limited to identify treatment effects that are clinically important but smaller than hypothesized and because Bayesian analyses can be used to estimate the (posterior) probability that laparotomy reduces death or NDI at 18-22 months.

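### The argument that examination will not reveal the arm at 18-22 months relies on later laparotomy being likely in both groups, which the protocol's own figures do not reliably support for the drain arm

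*Protocol*

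**What the plan says.** Protocol, Blinding and Reliability, gives two layers of protection. The first is procedural: "Follow-up personnel who are not told the treatment group will assess all follow-up findings". The second is an argument that the child's body will not give the arm away, because "patients in each treatment group are likely to require laparotomy after the initial surgical procedure" and "infants in both groups may have undergone multiple abdominal procedures". Three subcommittee members, unaware of the group, adjudicate outcomes that are uncertain. The SAP (Treatment Masking) repeats that evaluators are masked to operative details and adds no mechanism.

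Protocol, Follow-up Evaluation, lists a medical history and a "physical and neurological examination" at the same visit as the Bayley III. It refers to the Network follow-up protocol and manual for conduct.

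On how often drained infants go on to laparotomy, the protocol says several things:

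- Trial Justification, item 2: drainage spares only a minority of infants a laparotomy altogether.
- Issues Regarding Subsequent Laparotomy, Network observational study: "80 infants had an initial drain placement. Only 18 of these (22.5%) had a subsequent laparotomy".
- Same section, UK randomized trial: 26 of 35 (74%).
- Same section, NIH-funded randomized trial: 5 of 55 (9%) for early deterioration, with 16 further delayed laparotomies.
- Conclusions regarding subsequent laparotomy, items 1 and 2: uncommon, roughly 20%, when US surgeons choose the treatment, but possibly higher under randomization.

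**The concern.** The argument from later surgery works only if most drained children have also been opened by the time they are examined. Every child treated as assigned in the laparotomy arm has had a laparotomy. A child without one therefore points to the drain arm, and this is true at any later-laparotomy rate below 100%. Not telling the examiner the group does not remove that cue if the abdomen is seen or the surgical history is taken before scoring.

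The stake is the primary outcome. Protocol, Sample Size, assumes 50% mortality in each group and 80% versus 65% for death or NDI. With equal mortality, the planned difference must come entirely from NDI among survivors: (80 - 50)/50 = 60% versus (65 - 50)/50 = 30%. The cognitive score below 85 and the GMFCS level are scored by examiners. Adjudication is reserved for outcomes that are uncertain or lack information (SAP, NDI Adjudication), so it would not correct a completed score that had been influenced by knowledge of the arm.

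**Working it through.** **Step 1. Reproduce the stated rates.** 18/80 = 22.5%; 26/35 = 74.3%; 5/55 = 9.1%. All agree with the protocol. Adding the delayed cases in the NIH-funded trial gives (5 + 16)/55 = 38.2%, if all 16 were drain infants, which the text does not say outright.

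**Step 2. Share of surviving drain infants with no laparotomy.** Let n be group size and m mortality, both from Issues Regarding Subsequent Laparotomy:

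share = n(drain only) × (1 − m) / [n(drain only) × (1 − m) + n(drain then laparotomy) × (1 − m)], with each group's own m.

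- *Observational study* (62 at 55% mortality, 18 at 68%): 62 × 0.45 = 27.9; 18 × 0.32 = 5.76; 27.9/33.66 = 82.9%. A mortality of 68% is not attainable with 18 infants. Using 28 drain-only survivors and 12 or 13 deaths among the 18 gives 28/34 = 82.4% or 28/33 = 84.8%.
- *UK randomized trial* (9 at 49%, 26 at about 42%): 9 × 0.51 = 4.59; 26 × 0.58 = 15.08; 4.59/19.67 = 23.3%. With 4 or 5 deaths among the 9, the share is 5/20 = 25% or 4/19 = 21%. The 49% also equals 17/35 and may describe the whole drain arm; then 18 survived, 15 of them after laparotomy, and the share is 3/18 = 17%.
- *NIH-funded randomized trial*: the protocol gives neither drain-arm mortality nor survival after delayed laparotomy. Assume 50% mortality, so 55 × 0.5 = 27.5 survivors, 4 of them after early laparotomy. If all 16 delayed cases were drain infants and survived, (27.5 − 4 − 16)/27.5 = 27%. If half survived, (27.5 − 4 − 8)/27.5 = 56%. Varying mortality from 40% to 60% widens this to 9% to 64%.

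At base assumptions the three sources span about 23% to 83%.

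**Step 3. Accuracy of a guess from the abdomen.** Rule: no laparotomy means drain; laparotomy means laparotomy arm. Assume every child in the laparotomy arm has had a laparotomy, survivors are split equally, and the examiner can tell. The rule is right for all laparotomy-arm children and for a share p of drain children, so accuracy = (1 + p)/2.

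| Source | p | Accuracy |
|---|---|---|
| UK trial | 23% | 62% |
| NIH-funded trial | 27% to 56% | 64% to 78% |
| Observational study | 83% | 91% |

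The protocol plans 160 survivors and 90% follow-up, so 80 × 0.90 = 72 assessed drain children. Of these, about 72 × 0.23 = 17 to 72 × 0.83 = 60 would have had no laparotomy.

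**Step 4. What a lean would do (illustration only).** Assume cognitive scores near a mean of 85 with SD 15. The normal density at the cut-off is 0.399/15 = 2.66% of children per point. An assumed 3-point lean moves 3 × 2.66% = 8.0% of affected survivors across 85. With 50% survival, and the lean confined to drain children without a laparotomy, the shift in the drain arm's composite rate is 8.0% × 0.50 × p:

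- p = 23%: 0.9 percentage points
- p = 83%: 3.3 percentage points

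The planned difference is 15 points. A mean further from 85 gives somewhat less (about 2.3% per point at a mean of 93).

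**The case against.** A reader might infer that the protocol's own figures put 83% of surviving drain children without a laparotomy. They do not. That figure comes from one source, the non-randomized study in which surgeons chose the treatment. NEST is randomized, and the protocol expects that randomization may raise the rate of later laparotomy. The UK randomized trial gives 23%. The time window of the 22.5% is not stated, so operations up to 18-22 months may be uncounted. Trial Justification, item 2, also sides with the masking sentence. All of this stands, and 83% is the top of the base range.

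A reader might also infer that masking is missing, or stands or falls with the later-laparotomy sentence. The documents do not support that either. The main safeguard is that follow-up staff are not told the group. The sentence about later surgery is a supporting argument, and it is hedged.

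The route to bias is not documented. Certified psychologists or psychometricians give the Bayley, and nothing says they see the abdomen. The order of the visit is set by the Network follow-up manual, which is not among the documents and may already deal with this. The lean in Step 4, its size and its direction are assumptions. Applying it to every drain child would give about 4 points (8.0% × 0.50), but that treats all of them as identified, which none of the rates supports.

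A drain leaves a mark too, so having had no laparotomy does not mean an unmarked abdomen. That does not restore masking, because the cue is the absence of a laparotomy.

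**Conclusion.** The point holds as an internal inconsistency with a practical consequence. The blinding section treats later laparotomy as likely in each group. The evidence section gives drain-arm rates from 22.5% to 74%, with a mixed picture in the third source, and calls later laparotomy uncommon under surgeon choice. The sentence therefore cannot be relied on to protect the examiner-scored components of NDI. About 23% to 83% of surviving drain children may carry the cue, for a guess accuracy of about 62% to 91%. These are base-case figures; the alternative readings in Step 2 go lower for the two randomized trials.

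Whether any bias follows is unknown. The illustrative 0.9 to 3.3 points rest on an assumed 3-point lean, scores near 85 with SD 15, 50% survival and an examiner who sees the abdomen or learns the history before scoring. The direction could equally be the reverse. This is worth fixing because the remedy is cheap and NDI carries the whole planned effect, not because a bias has been shown.

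**What to change.** 1. Reconcile the rationale in Blinding and Reliability with Trial Justification, item 2, and with the rates and conclusions in the subsequent-laparotomy section.
2. Replace the later-laparotomy argument with a direct safeguard: keep the child's abdomen covered during the neurological and Bayley assessments, and leave the abdominal examination and surgical history until every NDI component has been scored. If the Network follow-up manual already requires this, cite it.
3. Optionally, have examiners record a guess of the arm after scoring, and tabulate the guesses by arm in the SAP.

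The cost is a small change to the standard Network visit order, some manual wording and, for item 3, one form item. It needs no additional staff or visit and leaves treatment untouched. If the assessments are already complete, correct the rationale and report possible unmasking of examiners as a limitation, giving the observed proportion of assessed drain children who had no laparotomy.
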